### 10.2 Statistical analysis

An ACIOS statistical analysis plan (SAP) will be written prior to inspection of the final dataset. Data will be presented at a continental African level. All institutional and national level data will be anonymised prior to publication. Categorical variables will be described as proportions and will be compared using

chi-square tests. Continuous variables will be described as mean and standard deviation if normally distributed, or median and inter-quartile range if not normally distributed. Comparisons of continuous variables between groups will be performed using t-tests, one-way ANOVA or equivalent non-parametric tests as appropriate. Univariate and hierarchical, multivariable, multi-level logistic regression models will be constructed to determine the relationship between the presence of critical illness and mortality and the relationship between essential emergency and critical care provision and mortality.

Results of logistic regression will be reported with 95% confidence intervals. The models will be assessed with predefined sensitivity analyses to explore possible interacting factors and examine any effect on the results. A single final analysis is planned at the end of the study.

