3.1 General analysis principles

Data will be presented at a continental African level. All institutional and national level data will be anonymised prior to publication. Categorical variables will be described as proportions and will be compared using chi-square tests. Continuous variables will be described as mean and standard deviation if normally distributed or median and inter-quartile range (IQR) if not normally distributed. No comparisons between groups will be performed at a univariate level.

For the analysis of the objectives, we will present the following information:

- The number of patients included in each analysis.
- Summary statistics of the outcome (e.g. median (IQR), mean (SD), number (%), range).
- A point estimate, odds ratio or hazard ratio with 95% confidence intervals.
- A two-sided p-value with a significance level of <0.05 will be used where relevant.

For data that are not necessary for each objective, imputation of missing observations will not be made and will be reported descriptively.

Statistical analyses will be performed using the Statistical Package for the Social Sciences (SPSS) version 28.0.1.1 (SPSS Inc., Chicago, IL, USA) and R (version 4.2.1) in RStudio (RStudio Team 2019).

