Statistical analysis plan for Objective 2 “*association between severity of pain and critical illness*”

Data on 'critical illness' will be extrapolated from the parent study ACIOS.

We will conduct univariate and multivariate logistic regression models to determine the association between severity of pain (continuous variable) and critical illness (binary variable). Severity of pain will be the independent variable and critical illness will be the dependent variable. The independent patient associated with critical illness identified in the primary paper will be included in the multivariate model. We will follow best practice by using both visual data analysis and formal modelling to investigate this relationship. The specifics of the models will be determined by the data features to achieve the best fitting model that is interpretable.

We will use a three-level generalized mixed model, with patients being at the first level, hospital at the second and country at the third level, to account for the expected correlation in outcomes within hospitals and countries.

3.7 Statistical analysis plan for Objective 3 “association between severity of pain and mortality”

The defined time for the outcomes is from the point of inclusion of the patient into the study to hospital discharge or death, censored at 7 days. Patients discharged alive are not followed up at home. Patients still in hospital receiving therapy at 7 days will be regarded as “alive” and included in the study.

We will conduct univariate and multivariable logistic regression models to determine the association between severity of pain (continuous variable) and mortality (binary variable). Severity of pain will be the independent variable and mortality will be the dependent variable. Additional patient factors identified in the primary paper to be independently associated with mortality will be included in the multivariate model. We will follow best practice by using both visual data analysis and formal modelling to investigate this relationship. The specifics of the models will be determined by the data features to achieve the best fitting model that is interpretable.

We will use a three-level generalized mixed model, with patients being at the first level, hospital at the second and country at the third level, to account for the expected correlation in outcomes within hospitals and countries.

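### Outside the regression models, the group comparisons named make no allowance for clustering by hospital, and no interval method is given for the co-primary proportions

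*Protocol*

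**What the plan says.** **Tests.** Protocol 10.2 says of categorical data: "Categorical variables will be described as proportions and will be compared using" chi-square tests (the sentence runs over a page break). For continuous data it says: "Comparisons of continuous variables between groups will be performed using t-tests, one-way ANOVA or equivalent non-parametric tests as appropriate". Neither sentence mentions hospital or country.

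**Where clustering is handled.** The same section continues: "Univariate and hierarchical, multivariable, multi-level logistic regression models will be constructed". These models address two relationships only: critical illness with mortality, and EECC provision with mortality.

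**Intervals.** "Results of logistic regression will be reported with 95% confidence intervals" is the protocol's only commitment to an interval. Prevalence of critical illness, 7-day in-hospital mortality (the co-primary outcomes, section 5.4) and EECC coverage have none. On reporting level it says: "Data will be presented at a continental African level".

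**Sampling.** Section 10.1 includes every eligible patient in each participating hospital and sets no sample size.

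**Pain sub-study SAP.** For Objectives 2 and 3 it uses a three-level model (patient, hospital, country) "to account for the expected correlation in outcomes within hospitals and countries". Section 3.1 says "Categorical variables will be described as proportions and will be compared using chi-square tests" and, later in the same paragraph, "No comparisons between groups will be performed at a univariate level". It also promises point estimates with 95% intervals, but names no clustered method beyond those models. Objectives 2 and 3 call for univariate logistic regressions, and Objective 3 adds a two-group log-rank test.

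**The concern.** A study that enrols whole hospitals is a cluster sample. Patients in one hospital share case mix, staffing, equipment and admission practice, so each adds less information than an independent patient would. Chi-square, t-test, ANOVA and rank tests take no account of this.

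Two things are at stake. First, EECC provision depends on resources that hospitals either have or lack, so it plausibly clusters by hospital. A table p-value for a factor of that kind would be too small. Second, the continental prevalence is the study's main figure, and an analyst following protocol 10.2 has no instruction on how to express its uncertainty. The usual default, a binomial interval, would overstate its precision.

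The sub-study SAP has a separate difficulty that needs no assumption. An analyst cannot both compare categorical variables by chi-square and make no univariate comparison between groups.

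**Working it through.** **Inputs.** The documents give no intraclass correlation (ICC), number of hospitals or patients per hospital, so there is no plan figure to reproduce. All three are assumed below. The 10% outcome is the background prevalence quoted in the protocol's Introduction and is not a design assumption. The nominal two-sided level is 5%.

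**Step 1: group comparisons.** Beta-binomial simulation with 100 hospitals of 100 patients, 10% outcome, no true difference, and 2,000 runs per cell. The test is the two-proportion z-test, which is equivalent to an uncorrected chi-square.

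| Factor compared | ICC 0.01 | 0.02 | 0.05 | 0.10 |
|---|---|---|---|---|
| Balanced within hospitals | 5.2% | 4.8% | 5.0% | 3.6% |
| Patient factor, own ICC 0.05 | 5.0% | 5.6% | 7.8% | 10.8% |
| Patient factor, own ICC 0.20 | 8.5% | 8.8% | 16% | 27% |
| Varies only between hospitals | 17% | 26% | 42% | 55% |

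Closed-form checks at outcome ICC 0.10, using type I error = 2(1 − Φ(1.96/√D)), where D is the variance ratio:

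- Between hospitals: D = 1 + (m − 1) × ICC = 1 + 99 × 0.10 = 10.9, giving 55.3%.
- Patient factor: D ≈ 1 + (m − 1) × ICC of outcome × ICC of factor. For factor ICC 0.20, 1 + 99 × 0.10 × 0.20 = 2.98, giving 25.6%. For 0.05, 1 + 99 × 0.10 × 0.05 = 1.495, giving 10.9%.
- Balanced: D ≈ 1 − ICC = 0.90, giving 3.9%.

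All agree closely with the simulation. Inflation depends on how strongly the factor itself clusters, and it is absent when the factor is balanced within hospitals.

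**Step 2: a binomial interval for prevalence, if one were used.** Design effect D = 1 + (m − 1) × ICC with equal hospital sizes. Actual coverage of a nominal 95% interval = 2Φ(1.96/√D) − 1.

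| Patients per hospital | ICC | D | SE understated by | Coverage |
|---|---|---|---|---|
| 50 | 0.01 | 1 + 49 × 0.01 = 1.49 | √1.49 = 1.2 | 89% |
| 50 | 0.05 | 1 + 49 × 0.05 = 3.45 | √3.45 = 1.9 | 71% |
| 150 | 0.01 | 1 + 149 × 0.01 = 2.49 | √2.49 = 1.6 | 79% |
| 150 | 0.05 | 1 + 149 × 0.05 = 8.45 | √8.45 = 2.9 | 50% |

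In absolute terms, for 100 hospitals of 100 patients, the binomial half-width is 1.96 × √(0.10 × 0.90/10,000) = 0.59 percentage points. Multiplied by √D it is 0.83 points at ICC 0.01 (D = 1.99) and 1.43 points at ICC 0.05 (D = 5.95). Unequal hospital sizes and country-level correlation would usually widen it further.

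**Step 3: a trap in the remedy.** Back-transforming the intercept of a logistic mixed model gives the prevalence in a typical hospital, not the proportion of inpatients. With a normal hospital effect on the logit scale and a true inpatient prevalence of 10%, the back-transformed intercept is 9.6% at ICC 0.01 and 8.3% at ICC 0.05. The model has to be averaged over its random effects.

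**The case against.** The strongest defence is that the associations the protocol singles out are already modelled with a multi-level structure. What remains is mostly p-values in descriptive tables, and a main-study SAP that could specify the rest is promised. The SAP to hand covers only the pain sub-study, so its gaps are not gaps in the main analysis. This stands, and it limits the point.

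Three stronger readings are tempting, and the documents do not support them.

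- A reader might infer that the published prevalence will carry an interval that is too narrow. Protocol 10.2 plans no interval for it, so the defect is silence, and the coverage figures describe only what a default choice would do.
- A reader might infer that every p-value outside the regressions is too optimistic. Factors balanced within hospitals show about 5% error or less.
- A reader might take 17–55% as the error rate of a planned test. No objective, research question or specified analysis schedules a comparison across hospital levels or types. The contrasts named are between patients: critically ill or not, EECC received or not, died or survived.

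The defence does not remove the fact that the protocol names unadjusted tests in general terms for any group comparison. Nor does it resolve the contradiction within section 3.1 of the sub-study SAP.

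**Conclusion.** The point holds in limited form. Protocol 10.2 names tests that assume independent patients in a study that samples whole hospitals, and it leaves the uncertainty of prevalence, 7-day mortality and EECC coverage unspecified. For patient-level factors that cluster by hospital, true type I error would be roughly 5–11% with modest clustering and 8.5–27% with strong clustering. These ranges rest on assumed ICCs, hospital numbers and hospital sizes, and the documents cannot narrow them. A binomial interval, if chosen, would cover between 89% and 50% for 50 to 150 patients per hospital and an ICC of 0.01 to 0.05.

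The conflict in the sub-study SAP rests on no assumption. The main-study SAP, which was not available, may already settle the protocol part.

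**What to change.** **Protocol 10.2 and the main-study SAP, comparisons.** Replace the chi-square, t-test and ANOVA comparisons with cluster-adjusted ones (Rao-Scott tests, or mixed models with hospital and country random effects), or present the tables descriptively without p-values.

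**Protocol 10.2 and the main-study SAP, intervals.** Give prevalence, 7-day mortality and EECC coverage 95% intervals by one of two methods:

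- a cluster-robust variance with hospital as the cluster, with country-level correlation checked; or
- a three-level model averaged over its random effects, so that it estimates the inpatient proportion.

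Treating country as a stratum is not equivalent to the three-level model, because it takes between-country variance out of the interval. It also fails where a country contributes a single hospital.

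**Pain sub-study SAP.** In section 3.1, delete the clause ordering chi-square comparisons and limit the ban on univariate comparisons to the descriptive tables. Without that limit, the ban still conflicts with the univariate regressions under Objectives 2 and 3 and the log-rank test under Objective 3. Make the log-rank comparison cluster-adjusted or descriptive.

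**Cost.** Changes of wording and standard commands in R, with no new data. Intervals will be wider and fewer p-values will be small.

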## 11. Ethical Considerations

The study will be carried out in accordance with the ethical principles in the International Conference on Harmonisation and Good Clinical Practice. Ethical approval will be obtained from the University of Cape Town with additional approvals in each country as required by national ethical committees, and from each institution as required by local regulatory requirements. Country Coordinators will be responsible for clarifying the need for ethical and regulatory approvals and for ensuring these are in place prior to data collection. Participating hospitals will not be permitted to record data without providing confirmation that the necessary ethical and regulatory approvals are in place.

The requirement for patient consent may vary according to national regulations. We anticipate that patient consent will not be required by most, or even all, nations on the basis that the study is, in effect, a large-scale clinical audit, the dataset will only include variables documented as part of routine clinical care, and identifiable patient data will not leave the treating hospital. Most importantly, critically ill patients are frequently unable to consent for themselves due to a decreased level of consciousness and a requirement of consent would exclude the very patients we most wish to help. Therefore, we will use 'broadcasting' signage informing patients and families that the site is participating in the study, if required by regulations to ensure patients are aware of the study (Appendix 1). A precedent for this approach was set internationally with the EuSOS and ASOS studies. In EuSOS, consent was waived in 27 of the 28 European countries participating, and in the ASOS-1 and ASOS-2 consent was waived in the majority of hospitals.

There is an ethical consideration when the study team observes a patient that is critically ill (see the Definitions section 8) requiring urgent care. On these occasions, the study team will immediately notify the clinical team about the patient's condition and provide them with the patient's vital signs. The treating clinicians will therefore be timely alerted to the status of the patient, and will be able to manage the patient according to local protocols. In each hospital, the study team will offer to document the patients' vital signs in the medical records – as in some low resource hospitals, patients' vital signs are not checked daily due to a lack of human or material capacity, so the project may contribute to an improvement to the standard of care.

As the data will only be submitted once the e-CRFs are complete, and the steering committee will only analyse the data after data collection is complete (and not in real time), the investigators will be unable to intervene in the clinical management of patients.

## 12. Safety considerations

There are no safety considerations relating to the study. There is no risk of harm to either patients or investigators.

## 13. Monitoring and Auditing

ACIOS study documents may be selected by the Sponsor to ensure study activities are conducted according to the protocol, the Sponsor's standard operating procedures, Good Clinical Practice and the applicable regulatory requirements. In participating hospitals, local study documents may also be selected for audit on a local basis. The ACIOS study team will not routinely monitor data collection in individual hospitals or conduct source data verification.

## 14. Study Committees

### 14.1 Study Management Team

ACIOS will be led by the Study Management Team who will be responsible for study administration, communication between project partners, data collection and data management.

## 14.2 Steering Committee

A Steering Committee will be responsible for overseeing the study and its scientific conduct.

## 14.3 Country Coordinators

Country Co-ordinators will be selected to lead the project within their country and:

- Identify hospitals and local co-ordinators in participating hospitals.
- Assist with translation of study paperwork as required.
- Ensure distribution of research manuals, data collection forms and other materials.
- Ensure necessary regulatory approvals are in place prior to the start date.
- Ensure good communication with the participating sites in the country.

## 14.3 Local Coordinators

Local co-ordinators in individual hospitals will have the following responsibilities:

- Provide leadership for the study in their hospital.
- Ensure all relevant regulatory approvals are in place for their institution.
- Ensure adequate training of all relevant staff prior to data collection.
- Supervise data collection and assist with problem solving.
- Act as guarantor for the integrity and quality of data collected.
- Ensure timely completion of e-CRFs.
- Communicate with the relevant national coordinator.

## 15. Dissemination and Publication Plan

The Steering Committee will appoint a writing committee to draft the ACIOS scientific report(s) which will be disseminated in a timely manner. The African Partnership for Perioperative and Critical Care Research (APPRISE) group authorship guidelines will be followed. It is anticipated that a number of secondary analyses will be performed. ACIOS investigators and coordinators will be given priority to lead such analyses and are encouraged to do so. Participation and authorship opportunities will be based on contribution to the primary study. The Steering Committee will consider the quality and validity of any proposed study, the statistical analysis plan, a data sharing agreement, objectives that are in-line with the wider aims of the ACIOS project, scientific validity and the possible effect on the anonymity of participating hospitals prior to granting any requests for additional studies. Where

necessary, a prior written agreement will set out the terms of such collaborations. The Steering Committee must approve the final version of all manuscripts including ACIOS data prior to submission, whether they relate to part or all of the ACOIS dataset. In the event of disagreement within the Steering Committee, the Chief Investigators will make a ruling. Any analysis incorporating ACIOS data from two or more study sites will be considered a secondary analysis and subject to these rules. The full study report will be submitted to the funder and will also be made accessible via clinicaltrials.gov.

## 16. Deliverables

The main deliverables will be scientific reports of findings for general and specialty journals, abstracts for presentation to national and international meetings including those of the supporting societies and a final report summarising the overall findings.

## 17. Finance and Funding

The ACIOS study is funded by the NIHR through the Global Health Group on Perioperative and Critical Care grant (NIHR133850). The funders will play no role in study design, conduct, data collection, data analysis, reporting or interpretation of the results.

## Appendix 2 – Case record forms (CRFs)

### 2a: Hospital level CRF

## African Critical Illness Outcomes Study (ACIOS) – Hospital CRF

### Section 1: Hospital characteristics

1. Language preference:  English  French  Arabic  Portuguese  Other .....

2. Hospital name: .....

3. Country: .....

4. Level of hospital:

First-level (e.g. district)  Second-level (e.g. Regional)  Third-level (e.g. University/Central/National)

5. Type of hospital:  Government  Private  Charitable

6. Total number of hospital beds: Total 

--	--	--	--

7. Number of beds in High Care Units: Total 

--	--	--	--

8. Number of beds in ICUs: Total 

--	--	--	--

9. Population served (catchment) of the hospital: 

--	--	--	--	--	--	--

## Section 2: Available Resources

Are the following available in your hospital?

	EQUIPMENT			
	Always	Sometimes	Never	Don't know
1				
2				
3				
4				
5				
6				
7				
8				
9				
10				
11				

	CONSUMABLES			
	Always	Sometimes	Never	Don't know
12				
13				
14				
15				
16				
17				
18				
19				
20				
21				
22				
23				
24				
25				

26	Gauze				
27	Intravenous cannulas of paediatric and adult sizes				
28	Intravenous giving sets				
29	Skin disinfectant for cannulation				
30	Syringes				
31	Nutrition				
32	Nasogastric tubes				
33	Lubricant for nasogastric tube insertion				
34	Intramuscular needles				
35	Intraosseous cannulas of different sizes				
36	Blankets				
37	Facemasks for Infection Prevention and Control				
38	Aprons or gowns				
39	Charts/notes for documentation				
40	Pens				

	DRUGS			
	Always	Sometimes	Never	Don't know
41				

42	Intravenous crystalloid fluids (eg. normal saline or Ringer's Lactate)				
43	Intravenous dextrose fluid (eg. 5%, 10% or 50%)				
44	Oxytocin				
45	Adrenaline				
46	Appropriate antibiotics				
47	Diazepam				
48	Magnesium sulphate				
49	Paracetamol				
50	Local anaesthetic (eg. 2% lignocaine) (eg. for intraosseous cannulation)				

	HR	Always	Sometimes	Never	Don't know
51	Health workers (eg nurses) with the ability to identify critical illness 24h/day				
52	Health workers with the (eg nurses) ability to care for critically ill patients 24hrs/day				
53	Senior health worker (eg doctor) who can be called to assist with the care of critically ill patients 24hrs/day				

	TRAINING				
	Always	Sometimes	Never	Don't know	
54	The health workers are trained in the identification of critical illness				
55	The health workers are trained in the care of critically ill patients				

  

	ROUTINES				
	Always	Sometimes	Never	Don't know	
56	The hospital has well-defined routines for the identification of critical illness				
57	The hospital has well-defined routines for managing critically ill patients				
58	There is a routine for the provision of EECC without taking into account patients' ability to pay				
59	There are routines for who and how to call to seek senior help 24hrs/day, 7 days/week				
60	There are routines for integrating EECC with other care including the definitive care of the underlying				

	condition (eg. use of condition-specific guidelines)				
	GUIDELINES		Always	Sometimes	Never
61	There are written guidelines for the identification of critical illness				
62	There are written guidelines for the essential care of critically ill patients				
	INFRASTRUCTURE		Always	Sometimes	Never
63	Designated triage area (area for the identification of critical illness) in the Out-Patient Department or Emergency Unit (area of the hospital where patients arrive)				
64	Running water				
65	Designated space for the care of critically ill patients (eg. a bay, ward, high care unit)				
66	Areas for separating and managing patients with a suspected or confirmed contagious disease from those without				

